8. SAFETY EVALUATION

8.1. Overview of Safety Analysis Methods

All safety analyses will be carried out on participants in the ITT sample. Screen failure data will be presented separately as specified below. Missing safety information will not be imputed. These analyses will not be stratified by site.

8.2. Adverse Events

All AEs will be classified by system organ class (SOC) and preferred term, according to a standardized thesaurus (Medical Dictionary for Regulatory Activities [MedDRA] version 18.0). The severity of AEs will be classified using the National Cancer Institute's (NCI's) Common Toxicity Criteria for Adverse Events (CTCAE) version 4.03. Each AE is entered on the electronic case report form (eCRF) once at the highest severity. As such, no additional data manipulation is needed to identify events.

An overall summary table will be developed to report the number of events and the number and percentage of subjects having at least one event in the following categories:

- All AEs
- AEs indicated as serious
- AEs with an outcome of death
- AEs that were reported as being related to immunosuppression withdrawal, blood draw, and/or biopsy
- AEs reported by severity
- AEs reported in >10% of subjects

In addition, AEs classified by MedDRA SOC and preferred term will be summarized overall for each of the following:

- All AEs

Summary tables will present the total number of events as well as the number and percentage of subjects experiencing the events. If a subject experiences the same AE on multiple occasions, the event will be counted once for each occurrence when reporting the number of AEs. When reporting the number of subjects experiencing the events, a subject will only be counted once if they experience an event within the particular SOC or preferred term. Percentages will be based on the number of subjects in the safety population.

A data listing will be provided for all AEs. A separate data listing will be presented for screen failures.

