1.4.1 Risks

1.4.1.1 Risks associated with Immunosuppression Withdrawal

The primary risk of immunosuppression withdrawal is that of graft rejection. Based on the studies detailed above, we anticipate that 50% of enrolled subjects will experience a rejection episode. Graft rejection carries three attendant risks: risk of irreversible graft injury or failure, the need for liver biopsy to verify the diagnosis, and the risk accompanying treatment(s) needed to reverse the rejection once the diagnosis has been secured.

- a. *Rejection associated graft injury or graft loss:* Given the high rate of expected rejection, the trial is specifically designed to allow early detection of rejection through frequent monitoring during the period of drug withdrawal and in the period early after immunosuppression cessation. Based on the experience of other withdrawal trials, with this approach it is expected that the majority of rejection episodes will be detected early and readily reverse. While theoretically possible, a severe rejection leading to graft loss, re-transplantation or patient death is very unlikely and has been only rarely observed with immunosuppression withdrawal in liver allograft recipients. In 4 separate studies of immunosuppression withdrawal on a total of 267 adult liver allograft recipients published between 1997 and 2013^{15,62-64} only a single graft loss was reported.^{62,63}.
- b. *For-cause liver biopsy risks:* Liver biopsy to permit histopathological assessment remains the gold standard in diagnosis of rejection and will be employed in all suspected cases of rejection in this trial unless clinically contraindicated or logistically infeasible. The procedure is usually performed percutaneously under ultrasound guidance and local anesthetic. It is usually associated with mild pain lasting only a few hours (rarely a few days). The risk of significant bleeding requiring transfusion is 0.5-1% and the risk of bile leak or injury to adjacent organs (pneumothorax, bowel perforation etc.) is even rarer and the risk of one of these complications leading to death is estimated at 0.1-0.01%.⁶⁵.

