2.2 SECONDARY OBJECTIVES

1. To determine the frequency of operational tolerance after liver transplantation.
2. To determine the safety of staged immunosuppression withdrawal in selected liver transplant recipients.
3. To determine the impact of immunosuppression withdrawal on:
 - a. Renal function
 - b. Changes in Quality of Life (QOL)
4. To describe the relationship between operational tolerance and recipient age.
5. To describe the relationship between operational tolerance and time post-transplant.
6. To describe the relationship between operational tolerance and miRNA expression profile in blood and liver tissue prior to withdrawal of immunosuppression.
7. To describe the relationship between operational tolerance and mRNA expression profile in blood and liver tissue prior to withdrawal of immunosuppression.
8. To evaluate the relationship between operational tolerance and serologic and molecular markers of iron metabolism.
9. To describe the relationship between operational tolerance and multi-parameter flow analysis for lymphocyte subsets.
10. To validate a previously defined liver tissue-based transcriptional signature of operational tolerance.
11. To describe the relationship between operational tolerance and donor specific T-cell reactivity in cases where donor or donor-type material is available.
12. To describe the relationship between operational tolerance and the gut microbiome.

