8.3.2 Attribution Definition

Adverse events will be categorized for their relation to each of the following:

- Study therapy: Immunosuppression withdrawal
- Study procedures (liver biopsy, blood draw)

The relationship, or attribution, of an AE to immunosuppression withdrawal or other study procedures will initially be determined by the site investigator and recorded on the appropriate case report form. Final determination of attribution will be determined by DAIT/NIAID. The relationship of an AE to the study therapy will be defined by using the descriptors provided in **Table 8**.

Table 8. Attribution of AEs

Code	Descriptor	Definition
UNRELATED CATEGORY		
1	Unrelated	The adverse event is definitely not related to the study treatment.
RELATED CATEGORIES		
2	Possible	The adverse event might or might not be related to the study treatment. (This grade is assigned when uncertainty exists)
3	Definite	The adverse event is definitely related to the study treatment.

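### The SAP's single related-AE category and undivided related-SAE endpoint give no biopsy-related rate, and screen failures' biopsy harms enter no rate at all

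*SAP*

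**What the plan says.** Protocol 8.3.2 sets up attribution by source: "Adverse events will be categorized for their relation to each of the following", after which it names immunosuppression withdrawal as study therapy and, as a second item, "Study procedures (liver biopsy, blood draw"). Protocol 1.4.1.1 treats rejection and biopsy as distinct risks and puts a number on the second: "The risk of significant bleeding requiring transfusion is 0.5-1"%.

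The SAP does not carry that separation into its tables. The overall AE summary in SAP 8.2 has one entry for related events: "AEs that were reported as being related to immunosuppression withdrawal, blood draw, and/or biopsy". The MedDRA tables are introduced by "AEs classified by MedDRA SOC and preferred term will be summarized overall for each of the following", and the list that follows has one item, all AEs. SAP 8.3 treats SAEs in the same manner. The study-related SAE endpoint in SAP Table 7-2, and its shell in the SAP Appendix, is one proportion with no split by cause.

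On population, SAP 8.1 states: "All safety analyses will be carried out on participants in the ITT sample". For candidates who never start withdrawal, SAP 8.2 adds: "A separate data listing will be presented for screen failures". Protocol 8.4.3 limits AE collection before withdrawal to events associated with protocol blood draws or the screening biopsy.

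**The concern.** One of the protocol's secondary objectives is "To determine the safety of staged immunosuppression withdrawal in selected liver transplant recipients". A reader judging it needs to distinguish harm from stopping the drugs from harm caused by study procedures. Attribution is recorded so that this can be done, but the related-event summaries merge the two sources.

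The sources differ greatly in frequency. Protocol 8.2.2 makes allograft dysfunction and rejection AEs, and Protocol 8.4.4 records them at any grade, while other events need grade 2 or higher. Protocol 1.4.1.1 anticipates rejection in 50% of participants; the earlier withdrawal trial described in Protocol 1.3.1 saw 58%. A participant who rejects and also has a biopsy complication counts once in the related category.

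Screen failures are a second gap. The screening biopsy is itself an eligibility test, and Protocol 3.1.1 puts no upper limit on screen failures. Some candidates will therefore be biopsied for the study and never join the ITT sample. By Protocol 8.4.3 any AE recorded for them is a procedure harm, yet it enters neither a numerator nor a denominator.

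**Working it through.** The plan states no figure for this category, so there is none to reproduce. As a check on the interval method, the exact 95% interval at n = 60 is 27.6-53.5% for 24/60 and 46.5-72.4% for 36/60, which matches Protocol 9.3.

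**Inputs from the documents**
- ITT size: 60 (Protocol 9.3).
- Rejection: 50% (Protocol 1.4.1.1) to 58%, i.e. 57/98 (Protocol 1.3.1).
- Bleeding needing transfusion: 0.5-1% per biopsy (Protocol 1.4.1.1).
- Protocol biopsies: one at screening, then years 1 and 3 after discontinuation (Protocol 3.1).

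**Assumptions**
- Every rejection is attributed to withdrawal.
- Rejection and biopsy harm are independent.
- There are 1 to 3 biopsies per participant. The central case is 2.5, about 150 in all: 60 screening, about 35 for-cause and about 55 at weeks 52 and 156.
- The central rejection figure is 55%.

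**Formulas**
- Risk of at least one biopsy event per participant: b = 1 - (1 - p)^k, with p the risk per biopsy and k the number of biopsies.
- Pooled related proportion: R = r + (1 - r) × b, with r the proportion with rejection.

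**Central case (r = 55%, k = 2.5)**

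| p per biopsy | b | R |
|---|---|---|
| 0.5% | 1.2% | 55.6% |
| 1% | 2.5% | 56.1% |
| 5% | 12.0% | 0.55 + 0.45 × 0.120 = 60.4% |

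The exact 95% interval for 33/60 is 41.6-67.9%. The SAP plans no interval for this row; it is used here only as a yardstick. A bleeding rate 5 to 10 times the protocol's figure stays well inside it.

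**Range over r and k, with p = 0.5-1% and k = 1 to 3**
- r = 50%: R goes from 50.0% to between 50.3% and 51.5%. The exact interval for 30/60 is 36.8-63.2%.
- r = 58%: R goes from 58.0% to between 58.2% and 59.3%.

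**What a separate display would show**
- Per participant, the expected number with a significant bleed is 60 × b, or 0.3 to 1.8. Exact 95% intervals are 0-6.0% for 0/60, 0.0-8.9% for 1/60 and 0.4-11.5% for 2/60.
- Per biopsy, 5% of the assumed 150 is about 7.5 events. Seven events in 150 give 1.9-9.4%, which excludes the protocol's upper figure of 1%. This treats biopsies as independent.

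**Screen failures.** Their number is not given. If 10 to 60 are biopsied, the expected bleeds at 0.5-1% are 10 × 0.005 = 0.05 up to 60 × 0.01 = 0.6. With them in a per-person denominator, one event has an upper limit of 7.7% (n = 70) down to 4.6% (n = 120), against 8.9% for 1/60.

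**The case against.** The strongest reply is that other displays do the job. The SOC/preferred-term table reports events and subjects for all AEs, and SAP 8.3 repeats it for SAEs. A procedural bleed would ordinarily code to a different term from rejection and get its own line. In the 5% scenario above, b = 12.0% is about 7 of 60 participants; if coded to one term, that would also exceed the SAP's category for events in more than 10% of subjects. The related category reports event counts as well as subjects, and every AE is listed. This stands: a reader might infer that a biopsy excess would be invisible, and the documents do not support that. What remains is that these displays are not by attribution and have no per-biopsy denominator.

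A reader might also infer that withdrawal harm is overstated. It is not: the category is openly labelled as covering three sources, and rejection, graft loss and death have their own endpoints with exact intervals in SAP Table 7-2.

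Nor does the SAP depart from the protocol. Protocol 9.2.3 promises tables by category of event, with related as an example, and a separate presentation of screen failures. No endpoint calls for a per-biopsy rate.

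Four smaller points also stand:
- No AE table shell is given, so sub-rows by attribution are not excluded, only unspecified.
- ITT participants' own screening-biopsy events are in the ITT tables. Only screen failures' events are listing-only, and that listing can be counted by hand.
- Protocol 1.4.1.1 counts the need for a biopsy among the risks that rejection brings, so for-cause biopsies are partly a consequence of withdrawal.
- Protocol 8.3.2 does not show that the CRF codes biopsy and blood draw separately.

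**Conclusion.** The point holds as a modest reporting improvement. As written, the related-AE category and the related-SAE endpoint do not separate withdrawal from procedures. The AE category will mostly measure rejection: at the protocol's own bleeding risk, biopsies add 0.2 to 1.5 percentage points to a base of 50-58%. No planned display gives a biopsy-related rate, and screen failures' biopsy harms enter none.

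The sizes rest on assumed biopsy counts, independence, attribution of all rejection to withdrawal, and transfusion-requiring bleeding as the only biopsy harm the protocol quantifies by type apart from death. Counting other dysfunction events as related would raise the base further; counting milder biopsy AEs would raise the biopsy share. If 5-10% of participants had any recordable biopsy AE (an assumption), the category would reach 52.5-55% from a base of 50%, still within 36.8-63.2%. For SAEs the masking is weaker, because mild rejection need not be serious, but the split is equally absent. The documents do not support the stronger conclusions that biopsy harm is hidden or that withdrawal harm is misreported.

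**What to change.** In SAP 8.2, SAP 8.3 and the display of the study-related SAE endpoint, keep the pooled total and add rows beneath it for withdrawal-related and procedure-related events. Show liver biopsy and blood draw separately where the CRF records them so. An event attributed to more than one source should count in each row and once in the total, with a footnote saying so.

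Add one table of biopsy-related AEs and SAEs per biopsy performed, with exact 95% confidence intervals and with protocol and for-cause biopsies shown separately. Screening biopsies of screen failures belong in both numerator and denominator. Because this table goes beyond the ITT sample, SAP 8.1 needs a sentence naming the exception.

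The cost is SAP wording and one extra table. Counts will be small and intervals wide, and the rate per biopsy ignores any clustering within participants. If the CRF codes procedures as a single category, the biopsy rows will need a review of attribution text. Trial conduct does not change.

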8.3. Deaths and Serious Adverse Events

Serious adverse events (SAEs) will be listed and summarized in the same manner described in Section 8.2. A separate display listing and summarizing death, including time of death relative to ISW and cause of death, will also be created.

8.4. Clinical Laboratory Evaluation

Clinical laboratory measurements include serum chemistry and hematology. Results will be converted to standardized units where possible.

Laboratory data will be plotted to show patterns over time for alkaline phosphatase, AST, ALT, GGT, total bilirubin, direct bilirubin, creatinine, WBC, and glucose. For these tests, data will be plotted as a spaghetti plot where each subject's values will be plotted and connected by line segments, forming one line per subject. All other tests will not be plotted.

8.5. Vital Signs, Physical Findings, and Other Observations Related to Safety

8.5.1. Vital Signs

Descriptive statistics of vital signs results will be summarized overall. Data listings sorted by subject, vital sign parameter, and time of assessment will be provided for vital signs measurements.

8.5.2. Physical Examinations

An indication of whether the examination was performed and the date of the examination were collected. Because details of events that are abnormal and meet AE reportable criteria will be entered on the medical history or AE form as appropriate, this data will be summarized with medical history and AEs, respectively.

8.5.3. Other Safety Measures

8.5.3.1. IS Minimization

The baseline IS dose (dose immediately prior to the initiation of withdrawal) will be compared to IS dose at the end of study participation for each subject that initiated IS withdrawal. Each comparison will be classified as 'more', 'less', or the 'same'. The count and percentage of each category will be presented.

For subjects that do not switch medication types (i.e. start on tacrolimus monotherapy and finish on tacrolimus monotherapy) this will be a straight numeric comparison of total daily dose.

For subjects on multiple drugs or subjects that switch medication types (i.e. start on tacrolimus and switch to cyclosporine), the SMT will complete a blinded review of the data and make a determination of 'more', 'less' or 'same'.

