3.1.3.5 Discontinuation of Immunosuppression Withdrawal/Resumption of Immunosuppression

- Participants undergoing immunosuppression withdrawal who experience biopsy-confirmed rejection will discontinue further withdrawal and be re-started on immunosuppression.

- Participants who have successfully completed immunosuppression withdrawal who subsequently experience biopsy-proven rejection will be re-started on immunosuppression.
- Participants with presumed rejection who are treated with increased immunosuppression without a confirmatory biopsy may undergo a biopsy within a week after treatment. If the biopsy is negative for rejection the participants may continue with immunosuppression withdrawal. If the biopsy is positive or suspicious for rejection, or if the participant is unable to undergo a biopsy, they will be considered to have failed immunosuppression withdrawal and will be resumed on immunosuppression.
- Participants who exceed 45 weeks (see section 3.1) to complete immunosuppression withdrawal will remain in the study but will be considered to have failed immunosuppression withdrawal.
- Participants who fail immunosuppression withdrawal will not be allowed a second attempt.
- Participants who cannot complete immunosuppression withdrawal and who do not experience rejection will remain in the study but will be considered as 'failures'.
- Any participant who has initiated immunosuppression withdrawal and subsequently terminates from this study prematurely **will not be** replaced.

Figure 3. Flowchart of Study Protocol

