7.2.1. Computation of the Primary Endpoint

A participant will be considered operationally tolerant if they have successfully withdrawn from all immunosuppression and remain off all immunosuppression for 52 weeks, have no evidence of rejection since enrollment, and have a liver biopsy at 52 weeks read centrally that shows both

the absence of rejection and has histological stability consistent with Table 1. Otherwise, the participant will be considered non-tolerant.

Participants who are non-evaluable at 52 weeks following discontinuation of all immunosuppression time point due to inadequate follow-up, lack of biopsy, or premature study termination will be considered non-tolerant for the purpose of evaluating the primary endpoint.

Biopsy results may be as early as 44 weeks following the discontinuation of all immunosuppression. This is because a for-cause liver biopsy visit that occurs within 8 weeks prior to a scheduled protocol visit takes the place of a scheduled protocol visit, thus a for-cause biopsy within 8 weeks of Visit 204 can be evaluated for the primary endpoint. Any biopsies done earlier than 44 weeks prior to discontinuation of all immunosuppression will be reviewed for inclusion by the SMT on a case by case basis. Any primary endpoint biopsy performed later than 52 weeks (+4 weeks) will be utilized.

All immunosuppression dosing information is collected as a daily record. Therefore, any immunosuppression information will not have an associated window.

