Changes in renal function (defined as estimated GFR calculated by CKD-EPI) in tolerant versus non-tolerant participants at 1, 2 and 3 years after completing immunosuppression withdrawal for tolerant subjects and failure of withdrawal for non-tolerant subjects.	
Baseline eGFR will be calculated from data collected at Visit 0. If Visit 0 data is missing, Visit -1 data will be used. Data collected closest to 1-year post completion/failure, within +/- 2 months, will be used to calculate eGFR at 1. The same process will be followed for 2 and 3-years after completion/failure.
 
eGFR will be calculated using the CKD-EPI equation:
 $\text{GFR} = 141 * \min(\text{Scr}/\kappa, 1)^\alpha * \max(\text{Scr}/\kappa, 1)^{-1.209} * 0.993^{\text{Age}} * 1.018 \text{ [if female]} * 1.159 \text{ [if black]}$ 
Scr: serum creatinine (mg/dL) κ: 0.7 for females and 0.9 for males α: -0.329 for females and -0.411 for males
 
Change in eGFR will be calculated as: 1-year post completion/failure eGFR – baseline eGFR
 
Thus positive value will indicate increase kidney function.
 
Changes will be summarized descriptively by tolerance status.
	ITT, PP
Changes in Quality of Life in tolerant versus non-tolerant participants and in all participants at baseline versus the end of study participation, as measured by the NIDDK Liver Transplantation Database Quality of Life Form.	The questionnaire filled out at Visit 0 will serve as the baseline questionnaire. The questionnaire filled out closest to the end of study participation will serve as the end of study questionnaire. For subjects	ITT, PP

	
with complete follow-up, this will be the questionnaire completed at Visit 208 or Visit 306.
 
The questionnaire will be summarized into five domains as outlined by Bell et al. The domains include measures of disease, psychological status, personal function, social and role function, and general health perception.
 
The change in each domain will be calculated as: Domain Score at End of Study – Domain score at Baseline.
 
The baseline, end of study, and change from baseline domain scores will be summarized descriptively by tolerance status.
 
If the data permits, a spaghetti plot visualizing each component score over time will be produced. Each graph will have two panels—one depicting the tolerant subjects, the other depicting the non-tolerant subjects.
	

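### SAP 8.5.3.1 pools end-of-participation dose for all initiators, so 'less' mixes people off all drug, people on a reduced dose and people who left mid-taper

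*SAP*

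**What the plan says.** SAP 8.5.3.1 defines baseline as the dose immediately before withdrawal begins; this "will be compared to IS dose at the end of study participation for each subject that initiated IS withdrawal". Each comparison becomes 'more', 'less' or 'same', and "The count and percentage of each category will be presented". For participants who keep the same type of medication, "this will be a straight numeric comparison of total daily dose". "For subjects on multiple drugs or subjects that switch medication types", "the SMT will complete a blinded review of the data and make a determination of 'more', 'less' or 'same'".

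Three other places settle how this works for people who leave early:

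- SAP Table 7-2 treats the end of participation as specific to each person. For the quality-of-life form, "The questionnaire filled out closest to the end of study participation will serve as the end of study questionnaire", and the final scheduled visit is named only for those with complete follow-up.
- SAP 7.2.1: "All immunosuppression dosing information is collected as a daily record". A dose at a mid-taper exit is therefore recorded rather than missing.
- Protocol 3.1.3.5 deals with "Any participant who has initiated immunosuppression withdrawal and subsequently terminates from this study prematurely": such a person is not replaced. SAP 8.1 runs safety analyses on the ITT sample, so early leavers stay in the denominator.

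Section 8.5.3.1 has no rule for early termination, no category for being off all drug and no split by tolerance status. The table shells in the SAP appendix include none for this measure.

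**The concern.** The measure stands among the SAP's safety measures under the label of minimisation. A reader will want to know two things from it: how many people who tried withdrawal ended on less drug, and whether those who failed ended on more than they started with. The pooled table answers neither cleanly.

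First, a participant who declines further follow-up, is lost or dies during the taper has a dose below baseline only because the taper was under way. Scoring that as 'less' reports a transient dose as minimisation. Someone who leaves while a rejection episode is being treated could likewise be scored on a temporary dose, in either direction.

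Second, 'less' combines people off all immunosuppression with people on a reduced dose. Most tolerant participants should be off drug. So may some non-tolerant ones: Protocol 6.9 does not require a restart after unfavourable week-52 histology, and SAP 7.2.1 counts a participant without the week-52 biopsy as non-tolerant whatever the dose. The outcome of a failed attempt therefore cannot be read from the table.

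**Working it through.** **Inputs from the documents.** 60 initiators, with planning tolerance of 40% and an alternative of 60% (Protocol 9.3). 30% is the lower end of the 30–40% success range expected in Protocol 1.3.2. Tolerance status is fixed at 52 weeks off drug (SAP 7.2.1), while the last scheduled visit is at week 156 (Protocol Appendix 2).

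**Assumptions.** All counts below of people ending on more, same or less, and of people leaving. The documents give none of them.

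**Step 1, anchor.** The plan states no figure for this measure. The planning figures do reproduce: the exact 95% interval is 27.6% to 53.5% for 24/60 and 46.5% to 72.4% for 36/60, as in Protocol 9.3.

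**Step 2, pooled 'more'.** Let t be the tolerant proportion, and m_T and m_N the shares ending on more among tolerant and non-tolerant participants. Then

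pooled 'more' = t × m_T + (1 − t) × m_N.

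If every tolerant participant ends off drug, m_T = 0 and the pooled share is (1 − t) × m_N. With m_N assumed to be one third:

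| t | non-tolerant | more / non-tolerant | pooled 'more' | factor |
|---|---|---|---|---|
| 30% | 42 | 14/42 = 33.3% | 14/60 = 23.3% | 0.7 |
| 40% | 36 | 12/36 = 33.3% | 12/60 = 20.0% | 0.6 |
| 60% | 24 | 8/24 = 33.3% | 8/60 = 13.3% | 0.4 |

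At t = 40% the exact 95% intervals are 10.8% to 32.3% (12/60) and 18.6% to 51.0% (12/36). If 4 to 18 of the 36 non-tolerant participants end on more (11.1% to 50.0%), the pooled figure runs from 6.7% to 30.0%.

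**Step 3, what changes the factor.** Suppose 2 of the 24 tolerant participants later restart and end on more. The pooled figure is (12 + 2)/60 = 23.3%. Dividing the pooled count by the number non-tolerant would give 14/36 = 38.9%, against a true 33.3%. Separately, if 4 of the 36 non-tolerant participants are off drug, 'more' among non-tolerant participants who are on drug is 12/32 = 37.5%.

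**Step 4, one printed table, three different results.** In each case 24 tolerant participants are off drug, 12 non-tolerant end on more and 18 on the same. The other 6 non-tolerant participants are (A) on a reduced dose, (B) mid-taper leavers, or (C) off all drug. The SAP table is identical each time: more 12/60 = 20.0%, same 18/60 = 30.0%, less 30/60 = 50.0%.

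**Step 5, leavers.** With 24 tolerant and off drug, L of the 36 non-tolerant leave mid-taper and the remaining 36 − L split evenly into more, same and less:

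| L | pooled 'more' | pooled 'less' | 'less' among all non-tolerant |
|---|---|---|---|
| 0 | 12/60 = 20.0% | (24 + 0 + 12)/60 = 60.0% | 12/36 = 33.3% |
| 3 | 11/60 = 18.3% | (24 + 3 + 11)/60 = 63.3% | 14/36 = 38.9% |
| 6 | 10/60 = 16.7% | (24 + 6 + 10)/60 = 66.7% | 16/36 = 44.4% |

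'Less' among non-tolerant participants who stay is one third throughout. One leaver adds 1/60 = 1.7 points to 'less' if that person would otherwise have ended on the same or more, and nothing if they would have ended on less anyway.

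**The case against.** The case for leaving the section alone has several sound parts.

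- Across everyone who tried withdrawal, the share ending on less, same or more is a coherent descriptive question. A fully weaned person is correctly on less, and the all-initiator denominator follows the SAP's own rule for safety analyses. This stands, and is why the overall total should be kept.
- The outcomes that the SAP splits by tolerance status (fibrosis, eGFR, quality of life, SF-36) are worded that way as protocol endpoints. Rejection, graft loss, mortality and study-related SAEs are pooled. So the missing split does not contradict the SAP's practice.
- Early exits may be few. Participants who cannot complete withdrawal stay in the study (Protocol 3.1.3.5), and those withdrawing consent before completion are asked to enter safety follow-up (4.3.1). Only people who decline, are lost or die mid-taper are affected.
- Disposition (SAP 5.1), the 3-year count of tolerant participants off drug (Table 7-2) and treatment changes per rejection episode (8.5.3.2) fill in part of the picture. None gives the final dose of participants who failed.

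Three stronger readings are tempting and are not supported. A reader might infer that all tolerant participants end at zero and can never be 'more'. But status is fixed at 52 weeks while dose is read at up to about week 156, and Protocol 6.8 and Appendix 4 provide for later restarts. A reader might infer that non-tolerant means back on drug; Protocol 6.9 and SAP 7.2.1 show otherwise. And a reader might fault the judgement used for multi-drug and switched regimens. That review is blinded, and nothing in the documents shows that it distorts the result. For a multi-drug leaver it also means that 'less' is likely rather than automatic.

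**Conclusion.** The point holds as a reporting weakness in a descriptive safety table. As written, a mid-taper exit dose is scored as if it were an outcome, normally 'less', and the 'less' category cannot be separated into its parts.

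The pooled 'more' share is 0.6 times the non-tolerant share at 40% tolerance (0.7 at 30%, 0.4 at 60%) only if no tolerant participant restarts. The 20.0% against 33.3% contrast rests on an assumed 12 of 36. The leaver effect has a known direction, but no known size, because no dropout rate is given.

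The measure is not in Table 7-2, carries no test or decision, and leaves the primary endpoint untouched, since non-evaluable participants are already counted as non-tolerant there. It is worth fixing because the change is cheap.

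**What to change.** In SAP 8.5.3.1:

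1. Add a category for participants off all immunosuppression at the end of participation, so that 'less' means a reduced dose.
2. Present the categories by tolerance status as well as overall, keeping the all-initiator total. Both this and the first change are needed, because neither tolerance status nor being off drug stands in for the other.
3. Show participants whose participation ended during the taper, or during treatment of a rejection episode, on a separate row, with their last recorded dose in a listing. State how the two periods are dated; the resolution rule in 8.5.3.3 could date the end of an episode for this purpose. Someone who stopped the taper and continued in safety follow-up is not in this row.
4. Keep the blinded SMT review for multi-drug and switched regimens.
5. Add a table shell.

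Under the revised rows the three cases in step 4 separate. Off all drug, reduced dose and early exit read 24, 6, 0 in case A; 24, 0, 6 in case B; and 30, 0, 0 in case C, with 18 on the same and 12 on more each time.

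The cost is SAP wording and one shell, with no new data and no change to patient management. A few participants move out of 'less' or 'more', and the table gains rows with small counts.
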